3.3 Inclusion of Women and Minorities

Both men and women of all races and ethnic groups are eligible for this trial. BRAF mutant melanoma is more common in Caucasians and women, though metastatic melanoma is more common in men.

Accrual Targets				
Ethnic Category	Sex/Gender			
	Females		Males	Total
Hispanic or Latino	1	+	1	= 2
Not Hispanic or Latino	18	+	18	= 36
Ethnic Category: Total of all subjects	19	(A1)	19	(B1) = 38 (C1)

Racial Category					
American Indian or Alaskan Native	0	+	0	=	0
Asian	1	+	1	=	2
Black or African American	0	+	0	=	0
Native Hawaiian or other Pacific Islander	0	+	0	=	0
White	18	+	18	=	36
Racial Category: Total of all subjects	19	(A2)	+	19	(B2)
		(A1 = A2)		(B1 = B2)	(C1 = C2)

4. REGISTRATION PROCEDURES

4.1 General Guidelines for DF/HCC and DF/PCC Institutions

Institutions will register eligible participants in the Clinical Trials Management System (CTMS) OnCore. Registrations must occur prior to the initiation of protocol therapy. Any participant not registered to the protocol before protocol therapy begins will be considered ineligible and registration will be denied.

An investigator will confirm eligibility criteria and a member of the study team will complete the protocol-specific eligibility checklist.

Following registration, participants may begin protocol therapy. Any laboratory values (chemistry and hematology) that are taken on C1D1 must re-meet eligibility in order for participants to receive treatment. Issues that would cause treatment delays should be discussed with the Overall Principal Investigator (PI). If a participant does not receive protocol therapy following registration, the participant's registration on the study must be canceled. Registration cancellations must be made in OnCore as soon as possible.

4.2 Registration Process for DF/HCC and DF/PCC Institutions

DF/HCC Standard Operating Procedure for Human Subject Research Titled *Subject Protocol Registration* (SOP #: REGIST-101) must be followed.

4.3 General Guidelines For Other Participating Institutions

Eligible participants will **NOT** be registered on study by the Coordinating Center. A designee from the institution will register patients with Theradex via the online slot reservation system, Interactive Web Response System (IWRS).

Prior to registration, a Site Investigator will confirm eligibility of prospective participants for all inclusion/exclusion criteria.

Following registration, participants should begin protocol treatment. Any laboratory values (chemistry and hematology) that are taken on C1D1 must re-meet eligibility in order for participants to receive treatment. Issues that would cause treatment delays should be discussed with the Principal Investigator/Sponsor. If a participant does not receive protocol therapy following registration, the participant's protocol status must be changed. The Coordinating Center should be notified of participant status changes as soon as possible.

4.4 Registration Process For Other Participating Institutions

External sites will only be registering patients to the protocol with Theradex via IWRS and not with DF/HCC. Sites will follow any site-specific processes as applicable.

The registration procedures are as follows:

- Obtain written informed consent from the participant prior to the performance of any protocol specific procedures or assessments.
- Verify all protocol eligibility criteria. **To be eligible for registration to the protocol, the participant must meet all inclusion and exclusion criterion as described in the protocol.**

Reminder: Confirm eligibility for ancillary studies at the same time as eligibility for the treatment protocol. Registration to both treatment and ancillary protocols will not be completed if eligibility requirements are not met for all studies.

- Designee will register patient with Theradex via IWRS.

5. TREATMENT PLAN

5.1 Agent Administration

Treatment will be administered on an outpatient basis. A cycle of treatment will be 28 days in length. IV administration will begin approximately the same time oral agents are dosed, but not more than 10 minutes after oral agents are taken. For Cycle days 8 and 15, patients will be instructed to bring oral agents with them to be given in the clinic. Patients are asked to maintain a medication diary for recording each dose of Dabrafenib and Trametinib (Appendix D).

Reported adverse events and potential risks are described in Section 7. Appropriate dose modifications are described in Section 6. No investigational or commercial agents or therapies other than those described below may be administered with the intent to treat the patient's malignancy. The patient will be requested to maintain a medication diary of each dose of medication. The medication diary (Appendix D) and pill bottles will be returned to clinic staff at the end of each course. To document compliance, a pill count will be performed of all unused pills.

Dosing levels for the study are listed below in Table 5.1. Dose level 1 will be the first dose level. Intrapatient dose escalation will be allowed when safe and feasible once the next higher dose level has been cleared. Additional, intermediate dose levels may be enrolled under the following

conditions:

- 1) Toxicity is seen at a dose level where dose modification is necessary and the prior, lower dose level was treated without DLT or analysis of the PK data suggests that an intermediate dose would be appropriate;
- 2) An intermediate dose is conceivable based on the size of pills and nature of the toxicity at the higher dose;
- 3) Consensus agreement is made between investigators, industry sponsors, and CTEP;
- 4) CTEP and IRB approval of an amendment to the protocol that clearly describes the rationale for and the logistics of the intermediate dose level.

Table 5.1 Dose Escalation Levels for Phase I Study

Dose Level	Dabrafenib [BID/PO]	Trametinib [QD/PO]	AT13387 [D1,8,15/IV]
-1	75 mg	1 mg	180 mg/m ²
1	150 mg	1 mg	180 mg/m ²
2	150 mg	2 mg	180 mg/m ²
3	150 mg	2 mg	220 mg/m ²
4	150 mg	2 mg	260 mg/m ²

5.1.1 Trametinib

The effect of food on trametinib absorption is unknown. The current recommendation is to administer trametinib on an empty stomach, either 1 hour before or 2 hours after a meal; the recommendation to administer trametinib fasting may change based on emerging data. Missed doses of trametinib should not be made up if there is less than 12 hours until the next scheduled dose. Vomited doses of trametinib should not be made up.

In the event that dabrafenib, AT13387, or both agents need to be discontinued due to toxicity reasons, treatment with trametinib may continue at the discretion of the investigator until time of disease progression.

5.1.2 Dabrafenib

Patients should take dabrafenib at least 1 hour prior to or 2 hours after a meal due to a potential food effect on dabrafenib absorption. Doses should be taken every 12 hours. Missed doses of dabrafenib should not be made up if it is less than 6 hours until the next scheduled dose (section 8.1.2). Vomited doses of dabrafenib should not be made up.

In the event that trametinib, AT13387, or both agents need to be discontinued due to toxicity reasons, treatment with dabrafenib may continue at the discretion of the investigator until time of disease progression.

5.1.3 AT13387

AT13387 is dosed in mg/m² using institutional standard of practice for dose calculations. AT13387 is administered via Infusion. Infuse over 1 hour through a central line or a well-defined peripheral vein (Note: an in-line filter is NOT required). If use a peripheral line, be sure to aspirate venous blood prior to starting the infusion. Check the

infusion site every 15 minutes and change the site of infusion should evidence of swelling or discoloration is observed. If AT13387 cannot be administered on Cycle Day 8 or 15, the dose will be skipped and not delayed.

If patient experiences pain along the infusion site, slow the infusion rate (i.e. > 1 hour duration) and/or infuse D5W through a “Y” connector. The additional volume of D5W dilutes AT13387 concentration at the local site of the infusion and alleviates the irritation.

In the event that trametinib, dabrafenib, or both agents need to be discontinued due to toxicity reasons, treatment with AT13387 may continue at the discretion of the investigator until time of disease progression.

5.2 Definition of Dose Limiting Toxicity

Dose-limiting toxicity (DLT) is based on the CTEP Active Version 5 of the NCI Common Terminology Criteria for Adverse Events (CTCAE). DLT refers to toxicities experienced during the first cycle of treatment between days 1-28. A DLT must be considered to be at least possibly related to study drug(s) will be defined as follows:

- Any grade 4 toxicity
- Grade 3 (or grade 2 intolerable) non-hematologic toxicity
- Grade ≥ 3 neutropenia with fever $> 38.5^{\circ}\text{C}$
- Grade 3 thrombocytopenia with clinically significant bleeding
- Furthermore, grade 2 intolerable/grade 3 fatigue that results in hospitalization should be considered a DLT.
- Intolerable AEs are toxicities deemed to lead to a missing dose of AT13387 or more than 25% of dabrafenib/trametinib in the first cycle.

In general, all Grade 3 or intolerable grade 2, non-hematological toxicities regardless of duration are considered DLT. However, the following Grade 3 toxicities will not be considered a DLT.

- The appearance of cutaneous squamous cell carcinoma or keratoacanthoma will not be considered a dose limiting toxicity as these are commonly observed with dabrafenib.
- Grade 3 fatigue persistent for ≤ 7 days
- Grade 3 nausea, vomiting, or diarrhea persisting ≤ 72 hours with maximum supportive care
- Grade 3 electrolyte events if they are resolved with replacement within 24 hours
- Lymphopenia regardless of grade
- The following grade 3 laboratory abnormalities will not be considered dose limiting if they return to baseline within 7 days: elevated bilirubin, AST, ALT, cholesterol, amylase, lipase, creatinine and hypertriglyceridemia

Management and dose modifications associated with the above adverse events are outlined in Section 6.

Dose escalation will proceed within each cohort according to the following scheme. Dose-limiting toxicity (DLT) is defined above.

Table 5.2. Dose escalation table

Number of Patients with DLT at a Given Dose Level	Dose Escalation Rule
0 out of 3	Proceed to the next dose level and enroll 3 patients
1 out of 3	Enroll and treat 3 additional patients at this dose level.
≥ 2 out of 3	Dose escalation will be stopped. The MTD will be one dose below this dose level. Three (3) additional patients will be entered at the next lower dose level if only 3 patients were treated previously at that dose.
1 out of 6	Proceed to the next dose level.
≥ 2 out of 6	Dose escalation will be stopped. The MTD will be one dose below this dose level. Three (3) additional patients will be entered at the next lower dose level if only 3 patients were treated previously at that dose.
If $\geq 2/3$ or $\geq 2/6$ patients at dose level 1 experience dose limiting toxicities, dose level -1 will be enrolled. If dose level -1 proves too toxic, the study will stop.	

5.3 General Concomitant Medication and Supportive Care Guidelines

5.3.1 Trametinib

Because there is a potential for interaction of trametinib with other concomitantly administered drugs through the cytochrome P450 system, the case report form must capture the concurrent use of all other drugs, over-the-counter medications, or alternative therapies. The Principal Investigator should be alerted if the patient is taking any agent known to affect or with the potential to affect selected CYP450 isoenzymes.

5.3.2 Dabrafenib

Because there is a potential for interaction of dabrafenib with other concomitantly administered drugs through the cytochrome P450 system, the case report form must capture the concurrent use of all other drugs, over-the-counter medications, or alternative therapies. The Principal Investigator should be alerted if the patient is taking any agent known to affect or with the potential to affect selected CYP450 isoenzymes. Appendix C is a patient information sheet that can be used for this specific protocol and presented to the patient.

Dabrafenib mesylate is a substrate for CYP 3A4, 2C8, p-glycoprotein (Pgp), and breast carcinoma resistance protein (Bcrp). Strong inhibitors/inducers of these enzymes and transporters are prohibited for eligibility and during the study.

Mild or moderate inhibitors/inducers of CYP 3A4, 2C8, Pgp, and Bcrp should be used with caution as dabrafenib serum concentrations may be altered. Because the lists of these agents are constantly changing, it is important to regularly consult a frequently-updated list such as <http://medicine.iupui.edu/clinpharm/ddis/table.aspx>; medical reference texts such as the Physicians' Desk Reference may also provide this information.

Dabrafenib may induce CYP 3A4, 2B6, and possibly 2C8/9 and 2C19. Use concomitant medications that are substrates of these isoenzymes with caution as there may be loss of efficacy. Substitute with other medications that are not affected if possible.

5.3.3 AT13387

AT13387 does not induce or inhibit the cytochrome P450 system, however the concurrent use of all other drugs, over-the-counter medications, or alternative therapies must be captured in the case report form. AT13387 is a substrate of UGT with a relatively low affinity for UGT isoforms. In vitro data demonstrate that AT13387 is a weak inhibitor of UGT1A1, UGT1A3 and UGT1A9. AT13387 is also a weak inhibitor of CYP1A2, -3A4, -2D6, -2C9 and -2C19. AT13387 metabolizes primarily via the glucuronidation, sulphation and N-oxidation. Use caution in patients taking CYP1A2, -3A4, -2D6, -2C9, -2C19 and UGT1A1, -3,-9 substrates with narrow therapeutic ranges. Caution should be exercised with all medications known to cause QTc prolongation or renal impairment since these events have been reported in previous studies with AT13387.

Supportive treatment should be given as per the institution standards and at the Investigator's discretion. In the presence of systemic infusion reactions, the infusion may be diluted to 500 mL and/or premedication given before subsequent infusions based on the systemic reaction symptoms (acetaminophen/paracetamol; antihistamines, dexamethasone, or similar agents for allergic manifestations; IV ondansetron or similar agents for nausea/vomiting). Antiemetics, anti-diarrheal agents, etc. may be given to treat or prevent gastrointestinal toxicities.

Subjects are advised not to drive or operate heavy machinery until they see how they react to the injections in terms of development of visual changes (i.e., at least during the first cycle of treatment).

5.4 Duration of Therapy

In the absence of treatment delays due to adverse event(s), treatment may continue until one of the following criteria applies:

- Disease progression,
- Intercurrent illness that prevents further administration of treatment,
- Unacceptable adverse event(s),
- Patient decides to withdraw from the study, or
- General or specific changes in the patient's condition render the patient unacceptable for further treatment in the judgment of the investigator.

The reason for removal from study treatment will be documented in the Case Report Form.

5.5 Duration of Follow Up

Patients removed from study treatment due to progressive disease will be followed for 4 weeks (28 days) after removal from study treatment or until death, whichever occurs first. Patients removed from study treatment for any reason other than progressive disease will be followed until disease progression or death, whichever occurs first. Patients removed from study for unacceptable adverse event(s) will be followed until resolution or stabilization of the adverse event or progressive disease, whichever occurs last. All patients will be asked to come to clinic for a follow-up visit 28 days (+/- 3 days) after last study treatment.

5.6 Criteria for Removal from Study

Patients will be removed from study upon completion of the follow-up phase (section 5.5), death or withdrawal of consent. The reason for study removal and the date the patient was removed must be documented in the Case Report Form.

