1.1.2 Secondary Objectives

1.1.2.1 To obtain preliminary estimates of the objective response rate (ORR) and progression-free survival (PFS) and document the 6-month PFS and 1-year overall survival (OS) of patients with BRAF-mutant metastatic or unresectable melanoma treated with AT13387 given weekly in combination with dabrafenib and trametinib.

1.1.2.2 To describe the pharmacokinetics of treatment with dabrafenib, trametinib, and AT13387.

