10. STUDY CALENDAR

Baseline evaluations are to be conducted within 14 days prior to start of protocol therapy. Scans and x-rays must be done \leq 4 weeks (28 days) prior to the start of therapy. Patients who are not being treated with AT13387 do not need to have Day 8 and Day 15 assessments done. In the event that the patient's condition is deteriorating, laboratory evaluations should be repeated within 48 hours prior to initiation of the next cycle of therapy. Participants will be required to maintain a diary (Appendix D) during each cycle and to bring the diary, unused pills, and all medication bottles to the day 1 visit of each cycle.

Procedure	Pre-Study	Cycle 1			Cycles 2+			End of Txt Visit	28 Day F-U Visit ³
	Baseline ¹	Day 1 ^{2,b}	Day 8 ⁴	Day 15 ⁴	Day 1 ²	Day 8	Day 15		
Dabrafenib and Trametinib ^A		DT ----- DT							
AT13387 ^B		X	X	X	X	X	X		
Informed Consent ^a	X								
Demographic	X								
Medical History	X	X	X	X	X				
Concurrent Medication	X	X	X	X	X				
Serum pregnancy test (B-Hcg) ^c	X								
Physical Examination	X	X	X	X	X			X	
Vital Signs (BP, HR, body temperature)	X	X	X	X	X	X	X	X	
ECOG Performance Status	X	X	X	X	X	X	X	X	
Dermatology Examination ^d	X				X				
Height	X								
Weight	X	X			X			X	
Ophthalmology Examination ^e	X				X				
12 Lead EKG ^f	X	X	X	X	X	X	X		
Hematology/Clinical Chemistry ^{g,p}	X	X	X	X	X	X ^p	X ^p	X	
Echo/MUGA ^h	X				X				
Coagulation ⁱ	X								
Tumor Measurements ^j	X								
Radiological Examination ^j	X							X ^j	
PK Analysis ^k		X		X					
Biopsies ^l	X		X					X	
Blood BRAF testing ^m		X		X	X			X	
AE assessment ⁿ	X	X	X	X	X	X	X	X	X
Long term Follow up ^o									

A. Dabrafenib and Tramatinib: doses as assigned; Dabrafenib BID and Trametinib QD.

B. AT13387: dosing as assigned per dose level.

1. All Prestudy assessments must be completed within 14 days prior to first dose, except for Scans and Echo that must be done within 28 days prior to first dose.

2. Assessment throughout the study is calendar based starting from first day of dosing (Day 1) in the first cycle of treatment. Dose interruptions should not alter the assessment schedule for any subsequent treatment cycle. Assessments and administration of study medication for each visit can be done within 3 days of the projected visit date. However, there must always be at least 6 days between AT13387 infusions.
3. Follow up visits should be 28 days from last dose of study drugs (\pm 3 days).

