 - a. Informed Consent can be obtained 28 days prior to the first dose
 - b. If within 3 days of screening, this assessment does not need to be repeated on Day 1 of the first dose
 - c. Serum Pregnancy test (Woman of childbearing potential only) done within 72 hours of first dose.
 - d. Dermatological Examination done at screening and then every 8 weeks (2 cycles)
 - e. Ophthalmological examination is done at screening, week 4, and annually; additional ophthalmic exams will be performed only as symptomatically warranted
 - f. Triple EKG will be collected at intervals according to the treating institution's standards prior to each AT13387 infusion
 - g. sodium, potassium, carbon dioxide/bicarbonate, BUN creatinine, glucose, calcium, magnesium, phosphorus, AST, ALT, total Bilirubin, Alkaline phosphatase, total protein and albumin, LDH, hematology includes CBC with differentials and platelets
 - h. Echo/MUGA is done at screening, week 4, week 12, week 24 and every 12 weeks thereafter.
 - i. Includes PT, PT-INR, PTT, repeated as indicated
 - j. Tumor measurements and radiological exam done every other (odd) cycle within 7 days of day 1 treatment. Documentation (radiologic) must be provided for patients removed from the study for progressive disease. Brain CT/MRI is required at baseline for patients with melanoma.
 - k. PK for phase 1: Cycle 1 Days 1 and 15; pre, 1, 2, 4, 6, 8, 24 hour post dose, Day 1 in Cycles 2, 4, 8, and 12.
 - l. In patients with biopsiable disease; pre treatment, Cycle 1 Day 8 (+/- 3 days), at disease progression (if possible)
 - m. Blood BRAF analysis performed C1 D1, C1 D15, at the beginning of each subsequent cycle and at disease progression.
 - n. AE assessment starting from the day 1 of dosing throughout the study
 - o. After 28 day follow up visit, patient is followed for survival only. Survival status is to be collected every 6 months (+/- 2 weeks) for up to 2 years and can be completed by phone. Patients removed from study treatment for any reason other than progressive disease will be followed until disease progression or death, whichever occurs first.
 - p. After cycle 6, hematology/clinical chemistry are collected on Day 8 and Day 15 at the investigator's discretion.

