Objective response rate is defined as the proportion of patients with complete or partial response as their best response to therapy. At the time of each restaging, patients will be classified as achieving complete response (CR), partial response (PR), stable disease (SD), progressive disease (PD), or non-evaluable for response according to RECIST (Version 1.1) criteria. Objective response will be determined by the best overall response designation recorded between the date of first dose of trial therapy and the date of objectively documented disease progression or cessation of trial therapy, whichever occurs first. For patients without documented progression or cessation of trial therapy, all available response designations will contribute to the objective response determination.

The distributions of progression-free survival (PFS) and overall survival (OS) will each be summarized using the product-limit method of Kaplan-Meier. Median times for each endpoint will be presented with two-sided, 90% confidence intervals estimated using log(-log(survival)) methodology. Kaplan-Meier estimates of 6-month PFS and 1-year OS will also be presented with two-sided, 90% confidence intervals.

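### Read literally, Sections 5.5 and 5.6 take patients off study before the survival contact in calendar footnote o; if OS is then censored at removal, 1-year OS is biased upward

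*Combined protocol and SAP*

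**What the plan says.** **Follow-up (5.5).** There are three rules, none of which mentions survival.
- Removal for progression: "Patients removed from study treatment due to progressive disease will be followed for 4 weeks (28 days) after removal from study treatment", or until death if that comes sooner.
- Removal for another reason: "Patients removed from study treatment for any reason other than progressive disease will be followed until disease progression or death, whichever occurs first".
- Removal for an unacceptable adverse event: follow-up runs to resolution or stabilization of the event or to progression, whichever is later. This can extend past progression.

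**Off study (5.6).** "Patients will be removed from study upon completion of the follow-up phase (section 5.5), death or withdrawal of consent". The reason and date go in the Case Report Form. The cross-reference is to 5.5 alone.

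**Study Calendar (Section 10).** There is a row for "Long term Follow up", explained by footnote o: "After 28 day follow up visit, patient is followed for survival only". It continues: "Survival status is to be collected every 6 months (+/- 2 weeks) for up to 2 years and can be completed by phone". The footnote then repeats the 5.5 sentence on patients who stop for reasons other than progression.

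**Endpoint.** Secondary objective 1.1.2.1 is to "document the 6-month PFS and 1-year overall survival (OS) of patients with BRAF-mutant metastatic or unresectable melanoma". Section 13.1 adds: "Kaplan-Meier estimates of 6-month PFS and 1-year OS will also be presented with two-sided, 90% confidence intervals". Section 13.3 repeats the 1-year OS estimate. Section 13 gives no censoring rule for OS.

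**The concern.** A patient who stops for progression completes the 5.5 phase about four weeks later, and 5.6 then takes that patient off study. Footnote o expects survival contact from about the same moment. Several institutions take part (4.3, 4.4), so sites can comply with different passages and supply different lengths of survival follow-up.

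Kaplan-Meier assumes that a censored patient has the same later risk of death as those still followed. Censoring shortly after progression breaks that assumption if progression raises the risk. Section 2.3 supports that direction for this disease: it describes accelerated progression and short survival once a BRAF inhibitor is stopped. The 1-year OS estimate would then be too favourable. A 28-day window also cannot supply 1-year survival status for anyone who progresses early.

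**Working it through.** **1. The plan's own precision figure.** Section 13.1 says that 90% exact intervals at n=14 are no wider than 0.48. The Clopper-Pearson width is largest at 7/14, where it is 0.473, so the statement is reproduced. The plan gives no expected 1-year OS to check.

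**2. Precision of 1-year OS at n=14.** With full follow-up, take 8 of 14 alive at 1 year as an illustration, S = 0.571. The log(-log) interval is S^exp(±z·se/|ln S|), with se = √[(1−S)/(nS)] = 0.231, z = 1.645 and |ln S| = 0.560. The exponent term is 0.680, and the limits are 0.331 and 0.753. Half-width = (0.753 − 0.331)/2 = 0.211, about 21 points.

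**3. Model for the bias.** Exponential illness-death model.
- Median PFS: 4, 5.8 or 9.4 months (5.8 and 9.4 from 2.2.2.3; 4 assumed).
- Median survival after progression: 3, 6 or 9 months (assumed).
- Share of PFS events that are deaths: 5%, 10%, 20% or 30% (assumed).
- Progression detected at the next 8-week restaging (Section 11 and 11.1).
- OS censored 28 days after detection for a share s of progressing patients (assumed); the others are followed fully.

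This gives 3 × 3 × 4 = 36 settings. With total PFS hazard λ = ln2/PFS median, progression hazard λ₁ = λ(1 − death share) and post-progression hazard μ = ln2/post-progression median, true OS is

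S(t) = e^(−λt) + λ₁(e^(−μt) − e^(−λt))/(λ − μ).

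For 5.8 months, 6 months and 10%: λ = 0.1195, λ₁ = 0.1076, μ = 0.1155, so S(12) = 0.238 + 0.315 = 0.553. The Kaplan-Meier value under censoring comes from simulation.

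| Setting, s = 100% | True 1-year OS | Kaplan-Meier | Bias |
|---|---|---|---|
| Smallest: 4, 9, 30% | 0.468 | 0.509 | +0.04 |
| Middle: 5.8, 6, 10% | 0.553 | 0.714 | +0.16 |
| Largest: 4, 3, 5% | 0.303 | 0.516 | +0.21 |

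| Share handled under 5.6 | Range over 36 settings |
|---|---|
| 100% | +4 to +21 points |
| 50% | +1 to +8 points |
| 25% | about +1 to +4 points (0.5 to 3.5 before rounding) |
| 0% | 0 |

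The bias was positive in every setting at each non-zero share.

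**4. Cross-check with other inputs.** PFS medians of 3, 5.8 and 9.4 months, post-progression medians of 3, 6 and 12 months, death shares of 5% and 15%, again with 8-week restaging and all progressing patients censored: +5 to +21 points in all 18 settings. With a median PFS of 3 months, the n=14 curve failed to reach 12 months in 23% to 30% of simulated trials.

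**5. Control.** With the same death hazard before and after progression, true OS and the censored estimate agree (0.435 and 0.435). The bias therefore comes from the rise in hazard at progression.

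**The case against.** The best defence is that the passages describe two phases: disease follow-up in 5.5, then survival contact in footnote o. The calendar row supports this, and footnote o gives an interval, a window, a duration and a method. That reading is reasonable, and under it there is no bias. What remains is that 5.6 ties off-study status to 5.5 by section number and does not mention footnote o, so a site can comply with 5.6 and still stop the calls.

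Three stronger readings are tempting, and the documents do not support them.

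- **That 5.6 ends all contact.** It does not say so. It says that the patient is removed and that the reason and date are recorded. The loss of survival data is a possible consequence, and the upward bias further requires that OS be censored at removal, which no passage states.
- **That the bias could reach +34 points.** The same 36 settings give +5 to +34 at full share only if progression is found the day it occurs. The protocol restages every 8 weeks, so progression is usually found later, more deaths are observed first, and the top of the range falls to about +21.
- **That the problem would be invisible.** Removal dates and reasons are recorded, so censoring clustered about four weeks after progression could be seen, and a curve stopping short of 12 months would be noticed. Seeing it would not restore survival status that was never collected.

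It is also fair to say that the 100% row would need every site to ignore an explicit calendar instruction.

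**Conclusion.** The inconsistency is in the current text and is worth fixing. Its effect on 1-year OS is conditional: a site must stop survival contact under 5.6, OS must be censored at removal, and the risk of death must be higher after progression. Given those conditions the direction is upward.

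The size is illustrative only, since post-progression survival, the death share of PFS events and the share of patients handled under 5.6 are all assumed. At a quarter share the bias is small beside the 21-point half-width; at full share it can equal it. One-year OS is a secondary, descriptive endpoint with no test or decision attached, and the MTD objective is unaffected.

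Two nearby matters are separate minor clarifications, and this point does not rest on them: how non-evaluable patients count in the response rate (11.1.1 against 13.1), and whether the efficacy estimates describe melanoma (1.1.2.1) or BRAF-mutant solid tumors (13.1).

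**What to change.** Reconcile 5.5, 5.6 and footnote o:

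- **5.5:** add the footnote o survival phase for every patient, whatever the reason treatment stopped. Keep the existing disease follow-up to progression for patients who stop for other reasons, so that PFS stays complete, and keep the existing adverse-event follow-up.
- **5.6:** let removal occur only at death, withdrawal of consent or the end of the 2-year survival period.
- **Footnote o:** label the repeated progression-or-death sentence as disease follow-up, distinct from survival contact.
- **Section 13:** state that OS is censored at the date last known alive.

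The cost is wording. The survival calls are already scheduled and can be made by phone, so no patients or visits are added. Reported 1-year OS may be lower than it would be under literal use of 5.6. Only survival data collection and analysis change; no dose or treatment rule is touched.
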